## 4. Ethics and quality

Prior ethics committee approval will be obtained before the start of this study.

It was important to obtain authorization for the use of the data before enrollment. To protect patient privacy, patient initials will be recorded on the CRF.

## **5. Data management**

Investigators were required to fill in the collected data into the case report form and collect or record the data in EXCEL according to the requirements of the study protocol. [name] was responsible for data management to ensure the authenticity, completeness and accuracy of the clinical trial data. At the end of the study, case report forms of all enrolled patients will be submitted to the data management center by the investigator. These case report forms should be completed and signed. Case-report form data collected from the sites will be checked for consistency, and question forms will be issued for inconsistent data, requiring investigator clarification.

## **6. Statistical analysis**

### **1. Statistical software**

The data were analyzed by a third party statistician who was not involved in the preliminary study. Statistical software (SPSS 26.0) was used for statistical analysis.

### **2. Description of data**

Measurement data were described by mean  $\pm$  standard deviation (), median, maximum, minimum and quartile, and enumeration data were described by percentage (%).  $\bar{x} \pm s$

### 3. Statistics of data

All the results were analyzed with the use of SPSS, version 23.0. All statistical tests were two-sided, and a  $P$  value of less than 0.05 was considered to indicate statistical significance. Normally distributed continuous variables were compared among the four groups using analysis of variance (ANOVA), and non-normally distributed variables were compared using the Kruskal-Wallis H test. If normal transformation could not be performed, the rank-sum test was used for comparison. Count data were compared using the chi-square test. Pearson correlation analysis was used for correlation analysis. Ordered logistics regression analysis was used to analyze the influence of general data on the final data. The factorial test focused on the main effects of the two treatments and their interaction. Therefore, repeated measures ANOVA with factorial design was used to analyze the differences in the effects of different treatments and different intervention acupoint areas on the observation area, and Sidak test was used for comparison between groups.

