### **3.2.5. Efficacy indicators and evaluation**

- (1) Baseline MEASURES: Through interviews and questionnaires, the subjects' gender, age, weight, height, frequency (weekly) of waist discomfort (such as waist acid, etc.), and whether they had received acupuncture/moxibustion related treatment were collected. Before the intervention, the average temperature of waist observation area (the geometric figure surrounding the second lateral line of bilateral bladder and the horizontal lines of T12 and S1) was recorded by infrared thermal imaging instrument.
- (2) The main outcome measures were the average temperature changes in the waist

observation area (the geometric figure surrounded by the second lateral line of bilateral bladder and the horizontal lines T12 and S1) 30 minutes after the intervention and immediately after the intervention

(3) Secondary outcome measures:

- ① The highest temperature in the designated area of the waist 30min after applying the intervention;
- ② The average temperature change value of the designated area of the waist was measured 5 min and 15 min after intervention.
- ③ The average temperature of local acupoints ( $\phi=2\text{cm}$ ) at Weizhong and Chize before intervention and 30 min after intervention were recorded.
- ④ Evaluation of waist warm sensation: Binary data (yes/no) and NRS score (0-10) were used to record the waist warm sensation and its intensity during the intervention.
- ⑤ The differences of pain threshold before rest and immediately after the intervention were compared at Shen双shu (BL 23), Zhishi臍 (BL 52), Mingmen (GV 4) and Weizhong (BL 40).

(4) Safety evaluation: the adverse reactions and their manifestations, occurrence time, degree, treatment measures, process and outcome were recorded, and the correlation

between the adverse reactions and the treatment was judged.

(5) Compliance evaluation: the drop-out situation and reasons were recorded and analyzed.

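### Section 6.3 applies one per-test P < 0.05 rule to every secondary reading, with no adjustment across secondary outcomes and no exploratory label

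*Combined protocol and SAP*

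**What the plan says.** Section 6.3 (Statistics of data) states that "All statistical tests were two-sided" and that a P "value of less than 0.05 was considered to indicate statistical significance". No outcome is exempt. The same section says "The factorial test focused on the main effects of the two treatments and their interaction", plans a repeated-measures ANOVA with factorial design for the observation area, and adds that "Sidak test was used for comparison between groups".

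Section 3.2.5 separates main from secondary outcomes. The main outcome is the change in average waist temperature. The five secondary items are:

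1. "The highest temperature in the designated area of the waist 30min after applying the intervention";
2. average waist temperature change, which "was measured 5 min and 15 min after intervention";
3. local temperature at Weizhong and at Chize;
4. waist warm sensation, as yes/no and as a 0 to 10 score;
5. pain threshold: "The differences of pain threshold before rest and immediately after the intervention were compared at" four points (BL 23, BL 52, GV 4 and BL 40).

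No section gives a testing order among these items, divides alpha between them, makes them conditional on the main result or calls them exploratory. The item headed Statistical Analysis Plan (section 6.4) says only who does the analysis and when.

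**The concern.** A single threshold for every test lets any secondary reading with P < 0.05 be reported as statistically significant, on the same footing as the main outcome. Several of these readings bear on the same question, a link between the waist and Weizhong: highest waist temperature, warm sensation, and pain threshold at three lumbar points. With several chances and no limit across them, an isolated significant result is much more likely to arise by chance than the 0.05 label suggests to a reader of the report.

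At stake is what the trial may declare about its secondary outcomes. The main analysis and the sample size are not affected.

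**Working it through.** **Plan's own figure.** The documents state no error rate across secondary outcomes, so there is none to reproduce. The only stated quantity is the per-test level, 0.05 two-sided (section 6.3).

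**Step 1: count the readings (section 3.2.5).**

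| Secondary item | Readings |
|---|---|
| 1. Highest waist temperature | 1 |
| 2. Average waist change, 5 and 15 min | 2 |
| 3. Local temperature, Weizhong and Chize | 2 |
| 4. Warm sensation, yes/no and score | 2 |
| 5. Pain threshold, four points | 4 |
| Total | 11 |

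A stricter count takes out readings that are not free-standing tests about the waist:

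- the 5 and 15 min values (2), which plausibly enter the planned repeated-measures ANOVA as time points;
- the two local acupoint temperatures (2), which are not waist readings and where a direct effect is expected;
- the BL 40 pain threshold (1), because BL 40 is Weizhong itself, the stimulated point in two arms.

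That leaves 11 − 2 − 2 − 1 = 6: highest waist temperature, two warm-sensation readings and three lumbar pain thresholds.

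**Step 2: independent readings.** With k true nulls and one 5% test each, the chance of at least one false significant result is 1 − 0.95^k.

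- k = 11: 1 − 0.95^11 = 43.1%
- k = 6: 1 − 0.95^6 = 26.5%

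**Step 3: correlated readings.** The documents give no correlations, so a common correlation ρ is assumed and varied. With equicorrelated standard normal statistics and c = 1.96, the chance is

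1 − ∫ φ(x) [Φ((c − √ρ x)/√(1−ρ)) − Φ((−c − √ρ x)/√(1−ρ))]^k dx.

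| k | ρ = 0 | 0.3 | 0.5 | 0.7 | 0.8 | 0.9 |
|---|---|---|---|---|---|---|
| 11 | 43.1% | 37.5% | 30.4% | 22.3% | 18.0% | 13.1% |
| 6 | 26.5% | 24.1% | 20.7% | 16.4% | 13.9% | 10.8% |

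**Step 4: check against the planned type of test.** A simulation of the four-group F test on 11 normal outcomes, 45 per group and 4,000 runs per setting, gave 44% at ρ = 0, 32% at 0.5 and 24% at 0.7. These are close to the k = 11 row.

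**Step 5: does Sidak cover this?** Section 6.3 names it for comparisons between groups, that is, among the arms within one outcome. It does not act across outcomes, so the rates above are not reduced by it.

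**The case against.** The strongest case on the other side has four parts.

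*No family-wise rate is promised.* A reader might infer that the plan claims 5% across the secondary outcomes and misses it. The documents do not support that: 0.05 is a per-test level. This part stands, and the point is only that nothing limits error across the set.

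*Eleven is an upper count.* The 5 and 15 min values plausibly belong to the repeated-measures model, the local temperatures are listed only as recorded, and BL 40 is not a waist site. This stands, and it is why the six-reading figure is given as well. In the other direction, a reader might apply three factorial effects to each reading and reach 33 tests, or 1 − 0.95^33 = 82% if all were independent. The documents tie the factorial model to the observation area and do not say that each secondary reading yields three separate claims, so that figure is not relied on.

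*A ranking exists.* Section 3.2.5 separates main from secondary outcomes, section 3.1.1 sizes the trial on waist average temperature, and the objective (section 2) refers to the same quantity. A reader might infer that a lone secondary result could carry the trial's conclusion when the main result is null. No section says so. What remains is that the plan does not rule it out and gives both tiers the same significance rule.

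*The aim is exploratory.* The objective is worded as exploring a relationship, in healthy volunteers, and unadjusted secondary P values are common in such work. This lowers the severity. It does not remove the mismatch, because the secondary outcomes carry no such label while section 6.3 applies the significance rule to them.

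**Conclusion.** The point holds as a low-severity gap. Section 6.3 lets any secondary reading be called statistically significant at P < 0.05, with no adjustment across secondary outcomes and no exploratory label.

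The chance of at least one false significant secondary result is 30% for 11 readings at an assumed correlation of 0.5 (18% at 0.8, 43% if independent), or 21% for the six waist readings outside the repeated-measures model (14% to 26% over the same range). Neither 30% nor 21% is a fact about this trial. Both rest on three assumptions: every counted null is true, each reading has one 5% test, and all readings share one correlation. Real effects on some readings would lower the rate. Equal correlation is also crude for the two warm-sensation readings, which measure the same sensation. The conclusion does not depend on the exact value, since every setting tabulated is above 10%.

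**What to change.** In section 6.3, replace the blanket rule with wording such as:

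> The P < 0.05 rule supports conclusions for the primary outcome only. Secondary outcomes 1 to 5 and the correlation and regression analyses are exploratory. They are reported as estimates with 95% confidence intervals and nominal P values. No secondary result is used on its own to conclude a relationship between the waist and Weizhong.

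A formal procedure for the secondary outcomes that depends on a significant primary test is not recommended as the plan stands. No single primary test is defined: section 3.2.5 names two primary time points, and section 6.3 names two main effects and an interaction.

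The cost is a few sentences, with no new data and no extra participants. The downside is that an isolated secondary P < 0.05 can no longer be called a significant finding.

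### The yes/no waist-warmth outcome has only a chi-square test with no stated contrast; read as a four-arm test, it cannot separate the effect of point from the effect of method

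*Combined protocol and SAP*

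**What the plan says.** Section 3.2.5 lists waist warm sensation as the fourth secondary outcome: "Binary data (yes/no) and NRS score (0-10) were used to record the waist warm sensation and its intensity during the intervention". The yes/no form is the only binary efficacy outcome in that list.

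Statistics of data (section 6, item 3) gives count data one sentence: "Count data were compared using the chi-square test". It does not say whether this means one 4×2 table, a 2×2 table by point, a 2×2 table by method, or pairwise tables. Just before it, continuous variables "were compared among the four groups using analysis of variance (ANOVA".

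The same paragraph states a factorial aim: "The factorial test focused on the main effects of the two treatments and their interaction". The only factorial model that it names is for the observation area: "repeated measures ANOVA with factorial design was used to analyze the differences in the effects of different treatments". The Sidak comparison is in that same sentence and is not assigned to count data. An ordered logistic regression is mentioned, but for the influence of general data on the final data, not for point or method.

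The Objectives section asks two things, both framed through waist temperature: how the waist relates to Weizhong, and whether acupuncture and moxibustion differ. Description of data adds percentages for count data. The item headed Statistical Analysis Plan adds no method.

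**The concern.** The trial crosses two factors, and each of its two questions is a contrast on one factor. A 4×2 chi-square has 3 degrees of freedom and tests only whether the four arms share one rate. If warmth differs by method and not by point, the test can still be significant, and the result could be reported as support for the Weizhong–waist link. If warmth differs by point and not by method, the test spreads that one difference over 3 degrees of freedom and loses power. In neither case does it produce an estimate or interval for the Weizhong-minus-Chize difference, so the yes/no outcome contributes little to either question.

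**Working it through.** **The plan's own figure.** Section 3.1.1 gives n = 2[(u_α + u_β)σ/δ]² + u_α²/4 with σ = 1.17, α = 0.05 two-sided and power 80%. With δ = 1.4 − 0.7 = 0.7 (acupuncture against moxibustion at Weizhong): 2 × [(1.960 + 0.842) × 1.17/0.7]² + 1.960²/4 = 43.85 + 0.96 = 44.81, rounded up to 45 per arm and 180 in total. This reproduces the stated size. It concerns temperature; no power is given for warmth.

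**Inputs.** From the documents: 45 per arm, 1:1:1:1 allocation, two-sided 0.05. Assumed, because the documents give no figure: warmth rates between 10% and 70%, and no dropout. Critical values are 7.815 (3 df) and 3.841 (1 df).

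**The two tests at expected counts.** The 4×2 statistic is Σ(x − 45p̄)²/[45p̄(1 − p̄)]. The stratified point test (Mantel-Haenszel) sums, over the two methods, the Weizhong count minus its expectation m/2, squares the sum, and divides by the summed variance 45²m(90 − m)/(90² × 89), where m is the number warm in that method.

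- Point effect only, Weizhong 40%, Chize 20%: counts 18, 9, 18, 9 and p̄ = 0.30. 4×2: 4 × 4.5²/9.45 = 8.57. Stratified: m = 27, variance 4.78 per method, so 9²/9.56 = 8.48. The evidence is almost the same, but one test sets it against 7.815 and the other against 3.841.
- Method effect only, 50% against 20%: counts 22.5, 22.5, 9, 9 and p̄ = 0.35. 4×2: 4 × 6.75²/10.24 = 17.8. The stratified point statistic is 0.

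**Rejection rates (200,000 simulated trials for each case).**

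| Assumed pattern | 4×2 chi-square | 1-df point test, stratified by method |
|---|---|---|
| Method only, 40% vs 60% | 61% | 5% |
| Method only, 20% vs 40% | 69% | 5% |
| Method only, 20% vs 50% | 96% | 5% |
| Method only, 20% vs 60% | 99.9% | 5% |
| Point only, 20% vs 35% | 45% | 62% |
| Point only, 30% vs 50% | 62% | 79% |
| Point only, 20% vs 40% | 69% | 84% |
| Point only, 30% vs 60% | 95% | 98% |
| Both (Chize to Weizhong: acupuncture 20% to 40%, moxibustion 50% to 70%) | 99.5% | 82% |

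With all four rates equal at 20% or 50%, the 4×2 test rejects in about 5%, as it should.

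**Patterns that follow the ordering in section 3.1.1** (acupuncture-Weizhong highest, then moxibustion-Weizhong, then the Chize arms). Rates are given as acupuncture-Weizhong / moxibustion-Weizhong / acupuncture-Chize / moxibustion-Chize, with 4×2 power against stratified point-test power:

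- 50/30/20/15%: 93% vs 93%
- 50/32/22/20%: 84% vs 84%
- 45/30/20/18%: 76% vs 80%
- 40/28/20/18%: 58% vs 63%

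The loss here is about 0 to 6 points.

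**The case against.** **The plan never says four groups for count data.** This stands. The phrase belongs to the sentence on continuous variables, and a 2×2 chi-square of Weizhong against Chize would fit the text and would itself be a 1-df point test. The four-arm reading is an inference from the design and the neighbouring sentence. On any reading, though, the contrast is unstated and no factorial analysis is assigned to this outcome.

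**The two harms need different scenarios.** This also stands. The power loss needs a point effect without a method effect, and false attribution needs a method effect. With both present, the omnibus test rejects more often than the point test (99.5% against 82%), but its rejections still cannot be attributed to point.

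**A reader might infer that moxibustion, as a heat treatment, is bound to raise reported waist warmth.** The documents do not support that. Heat is applied at the knee or elbow point while warmth is reported at the waist, and section 3.1.1 expects acupuncture to exceed moxibustion on waist temperature. The problem does not depend on direction: a method difference either way has the same effect.

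**A method-driven result is not irrelevant.** Whether the two methods differ is a stated objective. The difficulty is that the test cannot say which question it has answered.

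**Percentages by arm would be visible.** They would show the pattern to a careful reader, which reduces the risk of misreading. They do not supply a contrast or an interval.

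**Conclusion.** The concern holds as a gap with a better method readily available: yes/no waist warmth is assigned a chi-square with no contrast, and on the most natural reading that test answers neither factorial question and yields no effect estimate. On assumed rates with 45 per arm, a method-only difference gives significance in about 61% to 99.9% of the cases tried, and a point-only effect loses up to about 17 points of power. That loss shrinks to about 4 points at 30% against 60%, and to about 0 to 6 points under patterns like the plan's own ordering.

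Two stronger readings might be inferred and are not supported. One is that the chi-square inflates type I error: it holds 5% for its own null, and the fault lies in what the result can be taken to mean. The other is that a true point effect always loses about 15 points of power: that is a feature of certain assumed point-only patterns. The outcome is secondary, is also scored 0–10, and did not drive the sample size. The correction is worth making before analysis, but it does not bear on the primary outcome.

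**What to change.** For waist warmth, replace the chi-square sentence with:

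1. A 1-df test of point stratified by method, by Mantel-Haenszel or by a logistic model with effect-coded point and method.
2. The matching 1-df test of method stratified by point.
3. A separate test of the point × method interaction.
4. Risk differences for Weizhong minus Chize and acupuncture minus moxibustion, overall and within each level of the other factor, with 95% intervals.

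The coding must be stated. In a logistic model with an interaction and reference coding, the point coefficient compares the points within one method only (45 against 45). At 40% against 20% its power is about 53%, lower than the 69% of the 4×2 chi-square. Chi-square can stay for baseline tables.

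The cost is a short paragraph in the analysis section. SPSS, the software named in the plan, can fit the logistic form, and no data collection changes. The one drawback is that an exact or penalised version is needed if an arm has no or all warm responders, and the plan should say so in advance.

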## **2. Objectives of the study**

To explore the relationship between the waist and Weizhong points and whether acupuncture and moxibustion have different effects on the observation area of waist by observing the changes of local average temperature of waist in healthy subjects after applying acupuncture or moxibustion to different points.

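### The factorial analysis of waist temperature change does not use baseline temperature as a covariate; adding it would improve precision on the method effect and the interaction at almost no cost.

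*Combined protocol and SAP*

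**What the plan says.** Section 3.2.5 (Efficacy indicators and evaluation) has the baseline value recorded by infrared imaging: "Before the intervention, the average temperature of waist observation area". The region is the same as for the main outcome. That outcome is the change in mean waist temperature, timed at "30 minutes after the intervention and immediately after the intervention". A secondary outcome gives earlier times: "The average temperature change value of the designated area of the waist was measured 5 min and 15 min after intervention".

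The Statistics of data section names the model: "repeated measures ANOVA with factorial design was used to analyze the differences in the effects of different treatments". It states the target as well: "The factorial test focused on the main effects of the two treatments and their interaction". It lists no covariate. The only step relating subject characteristics to outcome is separate: "Ordered logistics regression analysis was used to analyze the influence of general data on the final data". That step puts no baseline term into the factorial model.

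The difference between methods is part of the stated objective, namely "whether acupuncture and moxibustion have different effects on the observation area of waist". Section 3.1.1 (Estimation of sample size) sizes pairwise comparisons and sets the interaction aside. Its planning table is headed Δ (°C), which also points to a change scale.

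**The concern.** A change score fixes the coefficient on baseline at 1. ANCOVA estimates it. Under equal variances and a correlation below 1 the best coefficient is below 1, so subtraction carries avoidable noise from the baseline image into the outcome. The trial collects the value needed to remove that noise and does not use it in this way.

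Precision is at stake, not bias. The contrasts affected most are the method effect, which is in the objective, and the acupoint-by-method interaction, which the analysis section says it focuses on. On the plan's own planning figures both fall short of 80% power at a single time point.

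**Working it through.** **Inputs from section 3.1.1.** Planned changes: Weizhong 1.4 (acupuncture) and 0.7 (moxibustion); Chize 0.3 and 0.2. SD 1.17, two-sided 5%, 80% power, 45 per group. The section does not say whether 1.17 is the SD of a change or of a single image.

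**Assumed, not in the documents.** Correlation rho between images of 0.3, 0.5, 0.7 or 0.9; equal variances.

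**Reproducing the plan's figure.** For the 0.7 °C contrast at Weizhong: 2[(1.960 + 0.842) × 1.17/0.7]² + 1.960²/4 = 44.8, so 45 per group, as stated.

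**Factorial contrasts.**
- Method: (1.4 + 0.3)/2 − (0.7 + 0.2)/2 = 0.4
- Acupoint: (1.4 + 0.7)/2 − (0.3 + 0.2)/2 = 0.8
- Interaction: (1.4 − 0.7) − (0.3 − 0.2) = 0.6

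The SE of a main effect is SD × √(2/90), and of the interaction SD × √(4/45). At SD 1.17 these are 0.174 and 0.349. Power is from the noncentral t with 176 df (175 with the covariate).

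**One time point, 1.17 as the SD of the change.** Var(ANCOVA)/Var(change) = (1 + rho)/2. Unadjusted power is 63% (method), 40% (interaction) and over 99% (acupoint). The unadjusted half-width of the method 95% CI is 0.34 °C.

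| rho | variance ratio | method power | interaction power | method half-width (°C) |
|---|---|---|---|---|
| 0.3 | 0.65 | 81% | 56% | 0.28 |
| 0.5 | 0.75 | 75% | 51% | 0.30 |
| 0.7 | 0.85 | 70% | 46% | 0.32 |
| 0.9 | 0.95 | 65% | 42% | 0.34 |

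**Three post-baseline images (5, 15, 30 min).** Further assumptions: equal correlation between all images and the same effect at each. The single-image SD is s = 1.17/√(2(1 − rho)).
- Mean post minus baseline: variance s²[(1 + 2rho)/3 + 1 − 2rho]. The SD is 0.955 at every rho, giving 80% power for method and 55% for interaction.
- ANCOVA on mean post: variance s²[(1 + 2rho)/3 − rho²].

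| rho | ANCOVA SD | variance ratio | equivalent n per group under change | method power | interaction power |
|---|---|---|---|---|---|
| 0.3 | 0.658 | 0.475 | 45/0.475 = 95 | 98% | 86% |
| 0.5 | 0.755 | 0.625 | 72 | 94% | 75% |
| 0.7 | 0.841 | 0.775 | 58 | 89% | 66% |
| 0.9 | 0.919 | 0.925 | 49 | 83% | 59% |

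At rho 0.9 this reading of 1.17 implies a single-image SD of 2.6 °C.

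**If 1.17 is the single-image SD (three images, s = 1.17).** The variance ratios are unchanged. Method power goes from 66% to 93% at rho 0.3, from 80% to 94% at 0.5 and from 95% to 98% at 0.7. It is above 99% either way at 0.9.

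**The case against.** The strongest reply is that baseline is already used. The outcome is a change, so the natural reading is that baseline is subtracted. A reader might infer that the plan ignores baseline or that its comparison is biased. The documents support neither inference: this is a valid change-score analysis compared with a more precise one.

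A reader might also infer that power collapses because baseline becomes a level of the repeated factor. With three post-baseline images and a constant effect, the time-averaged contrasts would then shrink to 3/4, or 0.30 °C instead of 0.40 for method. That requires raw baseline in the model despite a change outcome, and inference on time-averaged terms; group-by-time contrasts can be equivalent to change-score contrasts. No section says this will be done. It is a reason to word the model clearly, not a finding about the plan.

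Similarly, "If normal transformation could not be performed, the rank-sum test was used for comparison" does not say that rank tests replace the factorial model. Nor does the absence of a ranked primary time or model term carry this point.

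Three parts of the objection stand. The gain cannot be fixed from the documents, because rho is not given and 1.17 is not defined. The three-image schedule is an assumption: the two main-outcome times may be one or two, and with four images the unadjusted method power would be about 82%. Low interaction power is mainly a consequence of sizing on pairwise contrasts.

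**Conclusion.** The point holds as one of efficiency. Baseline waist temperature is collected and no covariate is planned. Under equal variances, ANCOVA is at least as precise as the change score apart from one degree of freedom. The variance reduction at one time point is (1 − rho)/2, from 35% at rho 0.3 to 5% at 0.9; with three images it is 52.5% to 7.5%. In power for the method effect, with 1.17 as the SD of a change, that is 18 points down to 2 at one time and 18 down to 3 with three images. On the single-image reading of 1.17 the power gain is effectively nil at rho 0.9.

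The acupoint effect is already well powered under subtraction and does not depend on this change. Adjustment is not a full remedy for the interaction: with 1.17 as the SD of a change it stays at 42 to 56% at one time, and with three images passes 80% only at rho 0.3 among the values tried. The direction is secure; the size rests on the assumed correlation, the reading of 1.17 and, for three images, on equal correlation and a constant effect.

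**What to change.** In the Statistics of data section, specify a linear factorial model with acupoint, method, acupoint × method, and baseline waist temperature as a covariate. Use ANCOVA if one image time is analysed, or a mixed model over the post-baseline images only if several are. The outcome can remain a change: with baseline as covariate, change and post-intervention temperature give the same treatment contrasts. State that baseline is not a time level in any time-averaged effect.

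The cost is one degree of freedom and the assumption of a common baseline slope across groups. No extra data or software is needed, only a change of wording, which should be made before group-level outcome data are seen.
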